2.2.13.3.1 Serious Adverse Events

The number and percentage of subjects experiencing a Serious Adverse Event (SAE) will be tabulated by SOC and PT within each treatment group and overall. SAEs will be counted only once for a subject within each PT and SOC.

2.2.13.3.2 Deaths

A listing of subjects who die while on study will be prepared along with the adverse event associated with the cause of death.

2.2.13.3.3 Interruptions or Discontinuations of Study Medication Due to an AE

A listing of subjects who have changes to their study medication dosing (dose reduced, interruptions or discontinuations) will be prepared.

2.2.13.4 Laboratory Data

Any laboratory test results considered to be clinically significant by the Investigator will be captured as an adverse event. All clinical laboratory values (haematology, biochemistry and urinalysis) will not be tabulated but will be listed for each patient by treatment group and visit. Values outside the laboratory normal ranges will be listed separately by patient and treatment group with associated comments as to their clinical significance.

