### **DS107 Cream Phase IIa Study in AD (DS107E-02)**

The study was a randomized, vehicle-controlled, double-blind, multi-centre Phase IIa trial to investigate the efficacy, safety, tolerability and bioavailability of three topically applied DS107 cream concentrations (0.1%, 1% and 5%) versus a matching vehicle in adult patients with mild to moderate AD. For all efficacy variables (change in mEASI, IGA, VAS, POEM and DLQI), there was a consistent trend of improvement from baseline over the study period (day 0 to day 28) for the 1% and 5% DS107 cream treatment groups. This trend of improvement displayed no evidence of treatment plateau, suggesting that greater and clinically significant improvement from baseline may be expected if treatment was to be continued for a longer time period. No SAEs were observed throughout the course of this study. The DS107 cream treatment groups were similar to the vehicle groups in terms of number of adverse events and event severity. No deaths or other SAEs occurred during the study.

Other than one strongly elevated CPK value in one patient (reported as not drug related AE) at the last visit in the 5% DS107 group, no clinically relevant treatment differences were seen in any of the laboratory parameter. In the vital signs parameters, the mean values were stable across treatment groups. Overall, DS107 cream appears safe and well tolerated, with a profile similar to vehicle.

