## 12.6 Data Analysis

Data analysis will be performed at the CRO. All computations will be completed using SAS® version 9.1.3 or later. Graphical summaries will be produced using SAS®. A detailed description of the analyses to be performed will be provided in the statistical analysis plan (SAP).

Continuous variables will be summarized in tables and will include the number of patients, mean, standard deviation, median, minimum, and maximum. Changes from baseline and percent changes from baseline will be evaluated for continuous endpoints. Categorical variables will be presented in tables as frequencies and percentages.

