## **12.8 Safety Analysis**

Demographic, medical history and physical examination data will be listed for each patient and summarised descriptively.

All AEs recorded during the study will be coded to system organ class and preferred terms using the current version of the Medical Dictionary for Regulatory Activities (MedDRA). AEs will be tabulated and summarised by treatment, relationship to treatment and severity.

Clinical laboratory values (haematology, biochemistry, and urinalysis) will be listed for each patient by treatment and day. Values outside the laboratory normal ranges will be listed separately with associated comments as to their clinical significance, with potentially clinically significant abnormalities highlighted and summarised by treatment. Clinical laboratory values obtained prior to dosing will be defined as baseline values.

Individual values of vital signs will be listed and summarised descriptively for each treatment and day.

---

Concomitant medications (if any), categorised by medication group and subgroup according to the latest version of the World Health Organisation drug dictionary, will be listed and summarised by treatment.

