2.2.13.3 Adverse Events

Counts and percentages of subjects who experienced any of the following will be presented by treatment group, as well as a total DS107 treatment group that includes both the 1% and 5% DS107 subjects: any AE, any IMP related AE, any AE requiring modification of study medication dosing (dose reduced, drug interrupted), discontinuations of study participation due to an AE (drug withdrawn), any serious adverse events (SAE), deaths, or IMP related SAEs. Only those adverse events determined to be treatment emergent (TEAE) will be presented (where Qlabel = "Treatment Emergent" from the SUPPAE SDTM dataset). Treatment emergent adverse events are those events with the date of AE onset being greater than or equal to the date of the first application date of study drug. A two-sided Fisher Exact test will be utilized for an overall global test and for the pair-wise comparisons of each treatment compared to vehicle.

Verbatim terms on the case report forms will be coded to preferred term (PT) and related system organ class (SOC) using MedDRA Coding Dictionary Version 19.1. The number and percentage of subjects who experience treatment-emergent adverse events (TEAE) will be tabulated by System Organ Class (SOC) and Preferred Term (PT) within each treatment group. The number of events will be tabulated by System Organ Class (SOC) and Preferred Term (PT) within each treatment group. In addition, a tabulation of adverse events that occur at a frequency of 2% or greater at the SOC or PT level will be prepared. A two-sided Fisher Exact test will be performed on system organ class (SOC) with a 2% or greater frequency to facilitate evaluation of potential safety differences among treatments.

Adverse events will be counted only once for a subject within each Preferred Term and System Organ Class; thus, since a subject may have more than one Preferred Term within an SOC, percentages of PT may not sum to the percentage in the SOC. If a Preferred Term is reported multiple times with differing severities (mild, moderate or severe), only the most severe is counted but all events will be counted. If a Preferred Term is reported multiple times with differing relationships to IMP, only the one that is related to IMP is counted.

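### The SAP tabulates no laboratory values, although Protocol 12.8 requires potentially clinically significant abnormalities to be summarised by treatment

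*SAP*

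**What the plan says.** Protocol 12.8 (Safety Analysis) sets out three laboratory outputs. The first is a listing of everything: "Clinical laboratory values (haematology, biochemistry, and urinalysis) will be listed for each patient by treatment and day". The second is a separate listing of out-of-range values with comments. The third is attached to the second: "with potentially clinically significant abnormalities highlighted and summarised by treatment". Protocol 12.6 (Data Analysis) adds a general rule, with no exception for laboratory data: "Continuous variables will be summarized in tables and will include the number of patients, mean, standard deviation, median, minimum, and maximum". It also says that changes from baseline will be evaluated for continuous endpoints.

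SAP 2.2.13.4 (Laboratory Data) keeps the two listings. All haematology, biochemistry and urinalysis values "will not be tabulated but will be listed for each patient by treatment group and visit". For abnormal results it says: "Values outside the laboratory normal ranges will be listed separately by patient and treatment group with associated comments as to their clinical significance". It stops there, without the summary by treatment. It gives one other route for laboratory findings: "Any laboratory test results considered to be clinically significant by the Investigator will be captured as an adverse event". Under SAP 2.2.13.3, treatment-emergent adverse events "will be tabulated by System Organ Class (SOC) and Preferred Term (PT) within each treatment group".

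**The concern.** The protocol commits to a by-treatment summary. The SAP's rule removes it without giving a reason; the revision history says only that the SAP was updated to reflect protocol version 5.0. Laboratory parameters are a safety endpoint in both documents, and the safety objective is to compare each DS107 strength with vehicle. A patient-level listing contains the data for that comparison but does not make it: it gives no number of affected patients, no denominator and no change by arm.

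What is at stake is how a safety endpoint is reported. If several patients in one arm had potentially significant values that no investigator considered clinically significant, no planned table would count them. The SAP plans no safety monitoring committee (2.2.7), so the final tables are the main place where such a pattern would be summarised.

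**Working it through.** No alpha, power or effect size is involved, and the plan gives no figure to reproduce. The check is a comparison of texts, followed by a count for scale.

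**Comparison**

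- All laboratory values. Protocol 12.8: listed. SAP 2.2.13.4: listed and expressly not tabulated. On the specific laboratory text the two agree about the listing. The SAP's ban on tabulation sits badly with the general rule in Protocol 12.6.
- Values outside the normal range. Protocol 12.8: listed separately with comments. SAP 2.2.13.4: the same.
- Potentially clinically significant abnormalities. Protocol 12.8: highlighted and summarised by treatment. SAP 2.2.13.4: nothing. This is the contradiction.
- Results the investigator judges clinically significant. SAP 2.2.13.4 makes them adverse events, and SAP 2.2.13.3 tabulates those by arm.
- Vital signs, for contrast. SAP 2.2.13.5 tabulates them by treatment group with change between baseline and end of study. The SAP therefore has no general policy of only listing continuous safety data.

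**Is the summary elsewhere in the SAP?** The remaining safety sections (2.2.13 to 2.2.13.5) and Appendix A contain no laboratory table, shift table or count of abnormalities by arm. Protocol 12.9 says the SAP will detail all analyses to be performed, so a table absent from the SAP is not planned.

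**Does the adverse event route replace it?** Only in part:

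- Clinically significant in the investigator's judgement is a narrower category than potentially clinically significant.
- The results are mixed with all other adverse events under their coded terms.
- The tables do not show how many patients had the test, nor any shift from baseline.

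**Scale**

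- Items in Protocol Table 2: 6 haematology (differential counted as one) + 10 biochemistry + 4 urinalysis = 20.
- Visits at which all patients are sampled (Protocol Appendix 1): screening, baseline and Week 8/early termination = 3. The Week 10 sample is conditional and is left out.
- Planned patients: about 300.
- Values that appear only in listings: 300 × 3 × 20 = 18,000.
- Of these, at Week 8: 300 × 20 = 6,000.

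Both are upper figures that assume no dropout and no missing samples.

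**The case against.** The strongest reply is that the gap is small. Protocol 12.8 itself only lists the full set of values, and its promised summary covers potentially clinically significant abnormalities, not every abnormality. Protocol 12.9.3, on safety variables, names only adverse event summaries. Investigators review and sign every laboratory report (Protocol 9.2.4), and results they judge significant reach the by-arm adverse event tables, with Fisher tests for system organ classes at 2% or more. The out-of-range listing is by treatment group, so a patient reader could count from it. The data are collected whatever the SAP says, and no efficacy result depends on them.

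Most of this stands as a limit on size. It does not remove the contradiction: 12.9.3 does not withdraw 12.8, and 12.8 asks for the laboratory summary in addition to the adverse event tables.

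A reader might infer three stronger points that the documents do not support:

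- *That there is no laboratory information by arm, or that a pattern cannot be found.* The adverse event tables carry some, and the listings identify treatment group. The listings are laborious to use, but they do not hide the data.
- *That Protocol 12.8 requires change-from-baseline and shift tables.* It does not.
- *That Phase IIa gives a specific CPK warning.* The protocol's account begins "Other than one strongly elevated CPK value in one patient". It concerns a single value at the last visit in the 5% group, reported as not drug related, and it says no other clinically relevant laboratory differences were seen. One extreme value captured as an adverse event is not evidence of a shift across an arm, and the point here does not rest on it.

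**Conclusion.** The inconsistency is real and should be corrected. The SAP removes, without a stated reason, a by-treatment summary that the protocol specifies for a named safety endpoint. By-arm laboratory information is left to what investigators judge clinically significant and report as adverse events, with no denominator of patients tested and no shift from baseline.

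The size is moderate. One protocol-specified output is missing for all 20 items in Protocol Table 2. The primary, co-primary and secondary efficacy analyses are untouched, and the table can still be produced from collected data. The conclusion rests on the wording of the two documents alone; it assumes no safety signal. The missing definition of potentially clinically significant is a gap in both documents, and it has to be closed before the required table can be programmed.

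**What to change.** In SAP 2.2.13.4, replace the statement that laboratory values will not be tabulated with a by-arm table on the Safety Analysis Set. For each parameter at Week 8/early termination it should give the number and percentage of patients with a potentially clinically significant value. Patients with a non-missing result should be the denominator, which is already the rule in SAP Appendix A, 4.2. State the criteria for each parameter in the SAP and fix them before unblinding. Keep both listings.

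As a supplement, justified by Protocol 12.6 and the comparative safety objective, add by-arm summaries of baseline, Week 8 and change for the quantitative parameters, and low/normal/high shift tables from baseline to Week 8/early termination.

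If the sponsor prefers listings only, amend Protocol 12.8 and state the reason in the SAP, so that the two documents agree.

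The cost is some extra programming and the work of agreeing criteria. No new data, visits or samples are needed.

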2.2.13.5 Vital Signs, Physical Findings, and Other Observations Related to Safety

Vital signs are collected at the screening, visit 2/baseline and the follow-up visits. Temperature (°C), systolic and diastolic blood pressure (mmHg) and heart rate (BPM) will be tabulated by treatment group using the baseline value (where baseline record flag= 'Y') and end of study (week 10). Change from end of study to baseline will be presented as descriptive statistics.

Physical Examination Findings will be presented in the listings but not tabulated.

Concomitant Medications will be coded per the WHO Drug dictionary (version effective March 2017 and provided to CTDS in the SDTM CM dataset. Concomitant Medications will be tabulated by treatment group,

Drug Class (pharmacological level, ATC3) and Drug Name (chemical substance level, ATC5). These data will be provided in subject data listings along with the verbatim drug term and usage details.

3 Document Version Control

Revision History:

REVISION	RELEASE DATE	AUTHOR	SUMMARY OF CHANGES
A	17Jul2017	CTDS/[name]	Initial Version
B	11Oct2017	CTDS/[name]	Updated SAP to reflect updated protocol version 5.0

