### **9.2.3 Vital Signs**

Vital signs measurements will be performed as per the Study Flow Chart (Appendix 1) at every visit. Measurements to be taken include:

- Blood pressure: will be performed as supine (after at least 5 minutes of rest) systolic and diastolic blood pressure (in mmHg)

- Heart rate: taken at rest (in bpm)
- Temperature: will be taken as per clinic practice. Temperature and route will be recorded in the CRF.

Vital signs measurements will be performed before any blood samples are taken. All new findings or changes to previous findings considered clinically significant will be recorded in the CRF as an AE if the finding is made after the patient has signed the ICF.

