Exploratory Endpoints	
 • Time to response by Week 8. • Probability of being in response (PBIR) between Weeks 2 and 8. • Sustained efficacy between Weeks 8 and 10. • Change from baseline in the Dermatology Life Quality Index (DLQI) score in the DS107 dose treated populations compared to vehicle population at Week 2, 4, 6, 8, 10, and last treatment visit and from Week 8 to Week 10. • Change from baseline in the Patient Orientated Eczema Measure (POEM) score in the DS107 dose treated populations compared to vehicle population at Week 2, 4, 6, 8, 10, and last treatment visit and from Week 8 to Week 10. • Change from baseline in the Patient Global Impression of Severity (PGI-S) score in the DS107 dose treated populations compared to vehicle population at Week 2, 4, 6, 8, 10, and last treatment visit and from Week 8 to Week 10. • Change from baseline in the Patient Global Impression of Change (PGI-C) score in the DS107 treated populations compared to vehicle population at Week 2, 4, 6, 8, and 10, and last treatment visit and from Week 8 to Week 10. • Determination of AD biomarkers in the DS107 dose treated populations compared to vehicle population at Baseline/Day 0 and Week 8/Early Termination (samples to be retained for the potential analysis at a later date).
Safety Endpoints	
 • Adverse event (AE) and serious adverse event (SAE) frequency and severity.

	
 • Safety laboratory parameters (haematology, clinical chemistry, urinalysis). • Clinical safety examinations (vital signs, physical examination).
Test Product, Dose and Mode of Administration	
All study medication will be blinded. DS107 cream will be provided as a cream containing either 5% or 1% DS107. Vehicle will be provided as a matching cream. This study will involve two dose levels of DS107 for 8 weeks (5% DS107 cream BD or 1% DS107 cream BD) and a vehicle control BD

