2.2.13.2 Safety Endpoint(s)

The safety objective is to compare the safety of topically applied DS107 cream (1% & 5%) versus vehicle, in the treatment of adult patients with mild to moderate AD. Results will be pooled for 1% and 5% as well.

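### SAP 2.2.13.5 tabulates vital signs by arm only at baseline and Week 10, so the treatment period has no group summary although Protocol 12.8 calls for one by treatment and day

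*SAP*

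**What the plan says.** **Collection.** Protocol 9.2.3: "Vital signs measurements will be performed as per the Study Flow Chart (Appendix 1) at every visit". The flow chart in Appendix 1 marks all seven visits. SAP 2.2.13.5 agrees: "Vital signs are collected at the screening, visit 2/baseline and the follow-up visits".

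**Summary planned in the protocol.** Protocol 12.8: "Individual values of vital signs will be listed and summarised descriptively for each treatment and day".

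**Summary planned in the SAP.** SAP 2.2.13.5 tabulates temperature, blood pressure and heart rate by arm at baseline and "end of study (week 10). Change from end of study to baseline will be presented as descriptive statistics". That is one post-baseline time point and one change score.

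**Status of the data.** The SAP's protocol summary names vital signs among the safety endpoints: "Clinical safety examinations (vital signs, physical examination"). The objective they serve is comparative. SAP 2.2.13.2: "The safety objective is to compare the safety of topically applied DS107 cream (1% & 5%) versus vehicle".

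**The concern.** The protocol asks for vital signs to be summarised over time in each arm. The SAP reduces this to one post-baseline point, and that point comes after treatment has stopped. If a cream strength moved blood pressure, heart rate or temperature while it was being applied, and the effect wore off afterwards, the planned table could show nothing.

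The rest of the objective safety data does not make up for this. Laboratory values are listed and not tabulated (SAP 2.2.13.4), and physical findings are listed only (SAP 2.2.13.5). Apart from adverse events, vital signs are the only safety endpoint with a summary table, and that table leaves out the treatment period. A patient who withdraws completely (Protocol 7.5.1) and does not return at Week 10 adds no post-baseline value to it, even if measured several times on treatment.

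**Working it through.** No power or error-rate figure is involved. The check sets the collection schedule against the planned tables, then dates the one tabulated visit.

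**Step 1. Visits collected and visits tabulated** (Protocol Appendix 1; SAP 2.2.13.5)

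| Visit | Nominal day | Relation to treatment | Measured | Tabulated by arm in SAP |
|---|---|---|---|---|
| Baseline | 0 | before first application | yes | yes |
| Week 2 | 14 | on treatment | yes | no |
| Week 4 | 28 | on treatment | yes | no |
| Week 6 | 42 | on treatment | yes | no |
| Week 8/ET | 56 | end of treatment | yes | no |
| Week 10 | 70 | off treatment | yes | yes |

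Screening is also measured but is not a post-baseline visit.

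- Post-baseline visits tabulated: 1 of 5.
- On-treatment visits tabulated: 0 of 3.
- End-of-treatment visit tabulated: 0 of 1.

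**Step 2. Gap from last application to Week 10**

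Protocol 8.2.7 and 10.3 put the last application on the day before Visit 6. SAP 2.2.5 gives Day 56 ± 2 for Week 8 and Day 70 ± 3 for Week 10.

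- Nominal: last application on Day 56 − 1 = 55; gap 70 − 55 = 15 days.
- Shortest, windows taken independently: last application on Day 58 − 1 = 57, Week 10 on Day 67; 67 − 57 = 10 days.
- Longest: last application on Day 54 − 1 = 53, Week 10 on Day 73; 73 − 53 = 20 days.

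Early terminators are asked back two weeks after their termination visit (Protocol 7.5 and 8.2.8), so their follow-up value is off treatment as well.

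**Step 3. Does anything else in the SAP fill the gap?**

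- SAP 2.2.12 provides summaries by visit, but for efficacy endpoints only.
- SAP 2.1 puts all data into patient listings sorted by site and subject. These show single values and do not summarise an arm.
- Appendix A of the SAP sets layout and number formats and adds no table.
- SAP 2.2.13.3 tabulates treatment-emergent adverse events by arm. Protocol 9.2.3 sends vital-sign changes there only when they are considered clinically significant.

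**Step 4. Direction of the change score**

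SAP 2.1 defines change as the post-baseline value minus baseline. The wording in SAP 2.2.13.5 runs from end of study to baseline. Read literally, that reverses the sign.

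**The case against.** A reader might infer that an on-treatment effect on vital signs would appear in no table at all. The documents do not support that. Under Protocol 9.2.3, changes considered clinically significant are recorded as adverse events. SAP 2.2.13.3 tabulates these by arm, system organ class and preferred term. It applies Fisher tests of each dose against vehicle to the summary categories, and Fisher tests to system organ classes at 2% or more. What escapes is narrower: a shift in arm means, or single changes that no investigator called significant.

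A reader might also infer that a promised between-arm comparison has been dropped. Protocol 12.8 promises a descriptive summary, not a test. The comparative wording belongs to the general safety objective, which does not prescribe vital-sign tables by visit.

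The practical risk also looks modest on the protocol's own evidence:

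- The 13-week minipig study found no significant systemic exposure after topical use (Protocol 1.5).
- Mean vital signs were stable across arms in the four-week Phase IIa study in atopic dermatitis (Protocol 1.6).
- The 12-week acne study at 1% and 5% raised no vital-sign concern (Protocol 1.6).

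No efficacy conclusion is touched, and the values stay in the database, so the tables could be produced later. Protocol 12.6 and 12.9 leave analysis detail to the SAP, so a narrower summary could be legitimate if it were explained.

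All of this limits the harm, and none of it closes the gap. The SAP gives no explanation, and reassuring earlier data are not a reason to leave the treatment period of this trial unsummarised.

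**Conclusion.** The point holds as a mismatch between protocol and SAP in safety reporting. A named safety endpoint, measured at five post-baseline visits, is summarised by arm at one of them, nominally 15 days after the last application (10 to 20 days across the visit windows). Weeks 2, 4 and 6 and the end-of-treatment visit have no group summary. The loss is confined to changes during treatment that investigators do not judge clinically significant. Those would be seen only by reading listings of about 300 patients.

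A reader might count Week 8 as a fourth on-treatment visit. It is better called end of treatment, because the last application is set for the day before.

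Two assumptions lie behind the dating, and neither changes the conclusion:

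- Week 10 is Day 70, as in the flow chart and SAP 2.2.5. SAP 2.1 describes the end-of-study visit as ten weeks after treatment, which does not agree with Day 70.
- The last application is the day before Visit 6. A parenthesis in Protocol 10.3 also lists Visit 6 among the visits where cream is applied after the assessments, which would make the gap 70 − 56 = 14 days. These statements should be reconciled.

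**What to change.** In SAP 2.2.13.5, tabulate each vital sign and its change from baseline by arm at Weeks 2, 4, 6, 8/early termination and 10, in line with Protocol 12.8. State the change as post-baseline minus baseline, as SAP 2.1 defines it, and remove the reversed wording. A row for the last on-treatment value is optional, since Protocol 12.8 does not ask for it. If the sponsor prefers the two-point table, the SAP should say that it departs from Protocol 12.8 and why.

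The cost is a few more rows in an existing table. No new data, visits or tests are needed.
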